3.2.3 Exploratory Objective Estimands

Exploratory objectives have efficacy, safety, and outcomes research endpoints. The estimands corresponding to the exploratory objectives are shown in [Table 3](#).

For each efficacy objective, intercurrent events are handled with a composite strategy described in Section 3.2. Subjects who take rescue medication are classified as failures for all efficacy assessments that are reported at or after taking rescue medication (see Section 6.3).

For efficacy endpoints, subjects with missing data at a time point are considered failures for the main estimand, whereas they are excluded for the sensitivity estimand (see Section 6.3).

Table 3: Exploratory Objective Estimands

Objective	Pain freedom at all time points postdose
Efficacy Endpoint	At each time point postdose, percentage of subjects with a pain intensity of none at the time point
Summary	Percentage of subjects with pain freedom over time by treatment group for the efficacy analysis set
Intercurrent Events	Rescue medication use at or before time point: Composite strategy, i.e., intercurrent event captured in endpoint definition
Objective	Pain relief at all time points postdose
Efficacy Endpoint	At each time point postdose, percentage of subjects with a pain intensity of none or mild at the time point
Summary	Percentage of subjects with pain relief over time by treatment group for the efficacy analysis set
Intercurrent Events	Rescue medication use at or before time point: Composite strategy, i.e., intercurrent event captured in endpoint definition
Objective	MBS freedom at all time points postdose
Efficacy Endpoint	At each time point postdose, percentage of subjects with MBS reported on study before dosing that is absent at the time point
Summary	Percentage of subjects with MBS freedom over time by treatment group for the efficacy analysis set
Intercurrent Events	Rescue medication use at or before time point: Composite strategy, i.e., intercurrent event captured in endpoint definition
Objective	Return to normal function at all time points postdose
Efficacy Endpoint	At each time point postdose, percentage of subjects with a functional disability level of normal at the time point for the subset with functional disability (mildly impaired, severely impaired, or requires bedrest) at the time of dosing
Summary	Percentage of subjects with return to normal function over time by treatment group for the efficacy analysis set

Objective	Pain freedom at all time points postdose
Intercurrent Events	Rescue medication use at or before time point: Composite strategy, i.e., intercurrent event captured in endpoint definition
Objective	Phonophobia freedom at all time points postdose
Efficacy Endpoint	At each time point postdose, percentage of subjects with phonophobia absent at the time point for the subset with phonophobia present at the time of dosing
Summary	Percentage of subjects with phonophobia freedom over time by treatment group for the efficacy analysis set
Intercurrent Events	Rescue medication use at or before time point: Composite strategy, i.e., intercurrent event captured in endpoint definition
Objective	Photophobia freedom at all time points postdose
Efficacy Endpoint	At each time point postdose, percentage of subjects with photophobia absent at the time point for the subset with photophobia present at the time of dosing
Summary	Percentage of subjects with photophobia freedom over time by treatment group for the efficacy analysis set
Intercurrent Events	Rescue medication use at or before time point: Composite strategy, i.e., intercurrent event captured in endpoint definition
Objective	Nausea freedom at all time points postdose
Efficacy Endpoint	At each time point postdose, percentage of subjects with nausea absent at the time point for the subset with nausea present at the time of dosing
Summary	Percentage of subjects with nausea freedom over time by treatment group for the efficacy analysis set
Intercurrent Events	Rescue medication use at or before time point: Composite strategy, i.e., intercurrent event captured in endpoint definition
Objective	MQoL
Outcomes Research Endpoint	Change from baseline in the total score at end of treatment visit
Summary	Mean change from baseline in total score by treatment group for the efficacy analysis set
Intercurrent Events	Rescue medication use: Treatment policy strategy, i.e., no accounting for intercurrent event
Objective	PoM
Outcomes Research Endpoint	Percentage of subjects who prefer study medication to previous migraine medications
Summary	Percentage of subjects in each category by treatment group for the efficacy analysis set with PoM data
Intercurrent Events	Rescue medication use: Treatment policy strategy, i.e., no accounting for intercurrent event
Objective	Safety and tolerability
Safety Endpoint	Frequency of adverse events (AEs) of at moderate or severe intensity, serious adverse events (SAEs), clinically relevant laboratory test abnormalities, and nasal inspection abnormalities
Summary	Number and percentage of subjects with safety events and findings for the safety analysis set
Intercurrent Events	Rescue medication use: Treatment policy strategy, i.e., no accounting for intercurrent event
Objective	S-STS
Safety Endpoint	Change from baseline in the total score at end of treatment visit
Summary	Percentage of subjects in each change from baseline category (< -1, -1, no change, 1, > 1) by treatment group for the safety analysis set with S-STS data
Intercurrent Events	Rescue medication use: Treatment policy strategy, i.e., no accounting for intercurrent event

4 ANALYSIS SETS, TREATMENT GROUPS, AND SUBGROUPS

4.1 Analysis Sets

The following analysis sets are evaluated and used for presentation and analysis of the data:

- **Enrolled:** Subjects who sign an informed consent form and are assigned a subject identification number, i.e., non-missing informed consent date.
- **Randomized:** Subjects in the enrolled analysis set who receive a randomized treatment assignment from the IWRS, i.e., non-missing IWRS randomization date.
 - **Efficacy:** Subjects in the randomized analysis set who (1) are randomized only once, (2) have a migraine of moderate or severe pain intensity at the time of dosing, (3) take study drug, and (4) have postdose efficacy data (i.e., non-missing pain intensity, phonophobia status, photophobia status, nausea status, or functional disability level with finding date/time from the eDiary Postdose Migraine Report).
- **Safety:** Subjects in the enrolled analysis set who take study drug (zavegepant or placebo), i.e., non-missing study drug start date/time.
- **Full:** Subjects in the randomized or safety analysis set.
- **Coronavirus Disease 2019 (COVID-19) impacted:** Subjects in the enrolled analysis set who are impacted by COVID-19 (see Section 9.1.2).

See Section 7.1 for derived dates.

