9 STATISTICS

9.1 Sample Size

It is anticipated that about 90% of the 700 subjects randomized to each treatment group will have a headache in the allotted time period, resulting in approximately 630 subjects evaluable for efficacy in each treatment group.

The sample size calculation is based on results from the Phase 2/3 dose-ranging study BHV3500-201. The response rates for the pooled zavegepant 10 mg and 20 mg groups, and for the placebo group in study BHV3500-201 were 22.8% and 15.5%, respectively, for pain freedom at 2 hours postdose, and 42.2% and 33.7%, respectively, for MBS freedom at 2 hours postdose.

A total sample size of 1,260 evaluable subjects (630 per group) will provide approximately 91% power for the co-primary endpoint of pain freedom at 2 hours postdose, approximately 88% power for the co-primary endpoint of MBS freedom at 2 hours postdose, and approximately 80% power to detect a difference between treatment groups for both endpoints jointly.

9.2 Analysis Sets:

- Enrolled: Subjects who sign informed consent and are assigned a subject identification number.
- Randomized: Subjects in the enrolled analysis set who receive a randomized treatment group assignment (zavegepant or placebo) from IWRS.
- Safety: Subjects in the enrolled analysis set who take study drug (zavegepant or placebo).
- Efficacy: Subjects in the randomized analysis set who: (1) are randomized only once; (2) have a migraine of moderate or severe pain intensity at the time of dosing; (3) take study drug; and (4) have postdose efficacy data (i.e., non-missing pain intensity, phonophobia status, photophobia status, nausea status, or functional disability level after taking study drug).

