6.2.3 Subject Disposition

Subject disposition is based on the Study Exit Status CRF, unless noted otherwise. Note that the Study Exit Status CRF links non-completion due to AE to the AE CRF using numeric variables.

In tables, reasons for not completing a milestone are displayed in alphabetical order. The reason of “other” for not completing a milestone is displayed as “other” without the corresponding specify text.

A by-subject listing of subject disposition is provided for the enrolled analysis set based on the Study Exit Status CRF, and includes the following: study completion status (yes, no); reason for not completing the study, including specify text for “other” and AE preferred terms (PTs); IWRS randomization date; study drug start date/time; last contact date; and previous subject identifier from the Informed Consent/Demographic CRF. The listing also identifies subjects who terminated the study prematurely due to COVID-19 (see Section 9.1.4). See Section 7.1 for derived dates.

A by-subject listing of eligibility with inclusion and exclusion criteria is provided for all subjects in the enrolled analysis set, not just those who have non-missing criteria. This is based on the Inclusion/Exclusion Criteria CRF.

See Section 7.1 for derived dates.

6.2.3.1 *Subject Disposition from Enrollment to Randomization*

Subject disposition from enrollment to randomization is tabulated for the enrolled analysis set as the number and percentage of subjects in the following categories:

- Randomized
- Not randomized
 - Reasons for discontinuation (i.e., not completing the study), including not reported. For subjects whose reason is screen failure due to inclusion/exclusion criteria, the reasons for screen failure are also included from the Inclusion/Exclusion Criteria CRF.
- Not randomized and terminated the study prematurely due to COVID-19 (see Section 9.1.4)
 - Reasons for premature termination, including not reported. For subjects whose reason is screen failure due to inclusion/exclusion criteria, the reasons for screen failure are also be included from the Inclusion/Exclusion Criteria CRF.

6.2.3.2 *Subject Disposition from Randomization to Treatment*

Subject disposition from randomization to treatment is tabulated for the randomized analysis set by as-randomized treatment group and overall as the number and percentage of subjects in the following categories:

- Treated with study drug (identified as those with non-missing study drug start date).

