The listing identifies the following: invalid kit IDs; subjects who took study drug, had a kit dispensed, but did not return a kit or had kit return status missing as per first cross-tabulation; and subjects with discrepant data as per second cross-tabulation, i.e., (1) eDiary study drug date/time is non-missing but IP not used or not reported, or (2) eDiary study drug date/time is missing but IP used.

An administrative listing of IP batch numbers is provided for the safety analysis set. Refer to the Zavegepant Core SAP for listing contents.

6.2.6.2 *Concomitant Non-study Medications*

The following non-study medications are tabulated by therapeutic class and preferred name and by as-treated treatment group for the safety analysis set:

- Concomitant medications: all; prophylactic migraine
- Rescue medications.

Concomitant and rescue medications are displayed in descending order of zavegepant frequency within therapeutic class and preferred name. Imputed medication start and stop dates are used to assign non-study medication type (previous, current, concomitant, or follow-up) to all non-study medications except rescue medications. Refer to the Zavegepant Core SAP for definitions of non-study medication types, non-study medication counting rules in frequency tables, and non-study medication start and stop date imputation.

Rescue medications are also tabulated by as-randomized treatment group for the efficacy analysis set to support efficacy.

A by-subject listing of non-study medications is provided by therapeutic class and preferred name for the enrolled analysis set. Medication types are identified. Prophylactic migraine and rescue medications are identified. Refer to the Zavegepant Core SAP for listing contents.

A by-subject listing of rescue medications is provided by therapeutic class and preferred name for the safety analysis set. The listing also displays the number of hours that rescue medication is taken from study drug.

Both listings display treatment day derived from the imputed start date and COVID-19 visit impact code for visits impacted by COVID-19 (see Section 9.1.5.2).

The following conventions apply to non-study medications:

- Non-study medications are identified from those reported on the Concomitant Medication and Rescue Medication CRFs. Note that the Concomitant Medication CRF links medical history and AE terms respectively to the Medical History and AE CRFs using numeric variables.

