7 CONVENTIONS

7.1 Derived Dates

Derived dates are defined as follows:

- Study drug start date/time: Earliest (1) study medication dose date and time from the eDiary Migraine Report, or (2) study medication intake date and time from the Study Medication Intake Report (see Section 7.5.1). This date is used to define analysis periods.
- Rescue medication start date/time: Earliest rescue medication date/time (see Section 6.2.6.2). Missing time is considered to be earlier than non-missing time on the same date.
- Imputed rescue medication start date/time: This is used only for time-to-event efficacy analyses in Section 6.3.4.3, and not for time to rescue medication use analyses in Section 6.3.3.8.
 - If the rescue medication start date and time are both not missing, then the imputed rescue medication start date/time is set to the rescue medication start date/time.
 - If the rescue medication start time is missing and the rescue medication start date is equal to the study drug start date, then the imputed rescue medication start date/time is set to the study drug start date/time.
 - Otherwise, if the rescue medication start time is missing and the rescue medication start date is equal to a postdose eDiary finding date with non-missing efficacy data, then the

imputed rescue medication start date/time is set to the first eDiary finding date/time corresponding to non-missing efficacy data.

- Otherwise, if the rescue medication start time is missing and rescue medication start date is equal to the study drug start date + 1 day, then the imputed rescue medication start date/time is set to the study drug start date/time + upper bound of the X -hour analysis window (see Table 5).
- COVID-19 visit date: (1) Complete visit date, if it exists; (2) otherwise, complete date the visit was planned to occur for a missed visit (see Section 9.1.1).
- Last contact date: (1) Earliest complete death date from AE CRFs, if it exists; (2) otherwise, the maximum complete date of the following: AE start or stop; COVID-19 visit only for in-person or remote visits; ECG; eDiary finding; eDiary study drug start; informed consent; IWRS randomization; laboratory collection; nasal inspection; non-study medication start or stop; physical measurement; procedure; rating scale; questionnaire; vital sign; visit. If the last contact date is after the most recent raw database creation date, then it is set to the most recent raw database creation date.

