- Death date: Last contact date derived only for subjects who died (see Section 6.4.1).

No date imputations are performed on these derived dates. Complete dates are those with valid, non-missing day, month, and year.

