7.2 Analysis Periods

Analysis periods are defined as follows:

- Pre-treatment: measurement date/time at or before the study drug start date/time. This period is used to derive baseline values and to assess pre-treatment endpoints. Note that all measurements are pre-treatment for subjects in the enrolled analysis set with missing study drug start date.
- On-treatment: measurement date/time after the study drug start date/time. This period is used to assess safety endpoints on treatment. Note that AEs with imputed start date equal to the study drug start date are part of this period.

See Section 7.1 for derived date/times for determining analysis periods.

If measurement time is missing, not collected, or not applicable for a parameter, then the measurement date is compared to the derived date.

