7.5.1 Study Medication

7.5.1.1 eDiary Migraine Report

If the subject answered “yes” to taking study medication mistakenly already before using the eDiary, then the eDiary Migraine Report collects study medication data based on when the subject reported taking study medication (today, yesterday, or other) as follows:

- Today: Study medication dose date is set to the finding date, and study medication dose time is collected
- Yesterday: Study medication dose date is set to the finding date – 1 day, and study medication dose time is collected
- Other: Only the study medication dose date is collected (time is missing).

The eDiary Migraine Report derives the study medication dose date and time from all available data.

Otherwise, if the subject answered “no” to taking study medication mistakenly already, had a current pain intensity of moderate or severe, and answered “yes” to confirming having taken study medication, then the eDiary Migraine Report derives the study medication dose date and time as the exact date and time the subject confirmed taking study medication (i.e., after the finding date/time).

7.5.1.2 eDiary Study Medication Intake Report

Subjects who took study medication without using the eDiary have the study medication date and time reported by the site on the eDiary Study Medication Intake Report.

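### A subject whose device is recorded as used but who has no recorded dosing date falls outside the safety set and out of every adverse event frequency table

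*SAP*

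**What the plan says.** Protocol 9.2 defines the safety set as "Subjects in the enrolled analysis set who take study drug (zavegepant or placebo"), with no condition on a recorded time. SAP 4.1 turns this into "Subjects in the enrolled analysis set who take study drug (zavegepant or placebo), i.e., non-missing study drug start date/time".

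SAP 7.1 derives the start date/time from the eDiary Migraine Report or the "study medication intake date and time from the Study Medication Intake Report", whichever is earliest. It adds that "No date imputations are performed on these derived dates".

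Sites also record on the Drug Accountability CRF whether the returned product was used (SAP 6.2.6.1). That section cross-tabulates this record against the eDiary and flags in a listing the subjects for whom "eDiary study drug date/time is missing but IP used". No later section acts on the flag.

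SAP 7.2 then states that "all measurements are pre-treatment for subjects in the enrolled analysis set with missing study drug start date".

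**The concern.** The SAP holds two records of dosing and lets only one decide who was exposed. Where the accountability record points to use and the eDiary reports hold no date, the SAP recognises the conflict but settles it by default in favour of no exposure. For a safety population this is the less cautious default, and it is narrower than the protocol's definition.

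At stake is the completeness of the exposed denominator and of the AE, laboratory, liver test and ECG summaries by arm. The subjects concerned dosed, if they did, outside the prescribed procedure, so they are not a random sample of those treated. No co-primary or secondary efficacy result depends on this point.

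**Working it through.** The point is about a derivation rule, so the main check follows one subject through the SAP: randomized, device returned and marked as used, no date in either eDiary report.

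1. **Start date/time (7.1).** Neither source holds a value, accountability is not a source, and nothing is imputed. The variable is missing.
2. **Safety set (4.1).** Not a member. The subject stays in the full set through randomization.
3. **Disposition (6.2.3.2).** Treated status is "Treated with study drug (identified as those with non-missing study drug start date"), so the subject is counted as not treated.
4. **Analysis period (7.2).** Every measurement is pre-treatment, including those from the End of Treatment visit.
5. **AE tables (6.4.1.2 to 6.4.1.4).** The overview, the pre-treatment tables and the on-treatment tables all use the safety set. The subject's AEs are therefore not moved to the pre-treatment tables; they enter no frequency table.
6. **Deaths (6.4.1.1).** A death would be tabulated under the not-treated heading.
7. **Narratives (6.4.6).** Those for on-treatment SAEs and events of special interest are limited to zavegepant-treated safety-set subjects. Deaths are covered for the whole enrolled set.
8. **What remains visible.** The AE and SAE listings (6.4.1) and the deaths listing (6.4.1.1) cover the enrolled set.

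**A subject with a date but no time.** A subject who reports dosing before using the eDiary and answers Other for the day has this recorded: "Only the study medication dose date is collected (time is missing"). Disposition in 6.2.3.2 needs only the date. SAP 6.2.6.2 has a branch for a missing study drug start time that works on the date. The all-pre-treatment note in 7.2 applies to a missing date and so does not reach this subject. Only 4.1 and 6.2.1 ask for a date/time, so the inconsistency is one of wording.

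**Size.** The documents give no count, so this is an illustration.

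- Randomized: 1,400. Expected to have a headache in the period: 90% (Protocol 9.1). Expected not to: 1,400 × 0.10 = 140. Taken as treated: 1,400 × 0.90 = 1,260.
- Assume a share s of a group of 140 counted as undosed had in fact used the device. The number left out is k = 140 × s, and its ratio to the treated is k / 1,260.
- SAE rate in BHV3500-201: two on-treatment subjects (Protocol 1.2.2.3) among 1,588 treated (Protocol 1.3.2), or 2 / 1,588 = 0.00126. Over 1,260 subjects this gives 1.6 expected. Among the k subjects left out it gives k × 0.00126.

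| s (assumed) | k | k / 1,260 | Expected SAEs among k |
|---|---|---|---|
| 1% | 1.4 | 0.1% | 0.002 |
| 5% | 7 | 0.6% | 0.009 |
| 10% | 14 | 1.1% | 0.018 |
| 20% | 28 | 2.2% | 0.035 |

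**The case against.** The strongest reply is that the main route into this case is already closed. SAP 7.5.1.2 has the site enter the dosing date and time for anyone who dosed without the eDiary, and mistaken early dosing is captured in the eDiary itself (7.5.1.1). Site staff review the handheld data at the End of Treatment visit and reconcile the returned drug. On this view the cross-tabulation and listing in 6.2.6.1 are a reconciliation check that runs in both directions, not a forecast of unresolved cases. This stands as a reason to expect few such subjects. It does not say what happens to those left after reconciliation, and for them 4.1 and 7.2 give a definite answer.

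A second reply is that a device marked as used does not prove a dose was received. That also stands. Protocol 7.2.2 and 8.1.5 anticipate incomplete sprays, malfunction and misadministration, and the SAP also flags subjects with a dosing date whose product is marked as not used. It is a reason to report these subjects visibly, not to count them silently as undosed.

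A third is that SAP 6.4 sends the slotting of safety data into periods to the Zavegepant Core SAP, which is not available here. It might contain an exception, but the wording of 4.1 and 7.2 is explicit and mentions none.

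Protocol 9.3 also leaves statistical detail to the SAP, so putting an operational definition on taking study drug is legitimate in itself. The difficulty is that this definition leaves out a case the SAP foresees.

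**Conclusion.** The rule, as written, misclassifies a foreseen group of possibly exposed subjects and is narrower than the protocol's safety set. It is worth correcting before database lock. The effect is probably small: under the assumed shares, about 1 to 28 subjects and well under one expected SAE. This rests on three assumptions: the assumed shares, the SAE rate from BHV3500-201 applying to these subjects, and no overriding rule in the Core SAP.

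A reader might infer more than the documents support:

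- **That the events disappear.** They do not. They remain in enrolled-set listings; what is lost is their place in the rates by arm.
- **That a subject with a date but no time is treated as undosed throughout.** Disposition and the 7.2 note both work on the date, so only the membership wording in 4.1 and 6.2.1 is unclear.
- **That one misplaced SAE is likely because only about 1.6 are expected.** One would indeed be a large share of the total, but the expected number misplaced is at most about 0.035 in the table above.
- **That counting every AE from dispensing as on-treatment would be conservative.** Subjects hold the device for up to 45 days, so this could add drug-free time to both arms and dilute a difference between them.

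**What to change.** 1. In SAP 4.1 and 6.2.1, base treated status on a non-missing study drug start date, time not required. This matches 6.2.3.2.
2. Add subjects whose product is recorded as used but who have no recorded date to the safety set and its denominators. Apply the same rule in 6.2.3.2, 6.2.3.3 and 6.4.1.1, and footnote their number by arm.
3. Exempt these subjects from the all-pre-treatment note in 7.2. Take baseline as the last value at or before randomization, which is the rule 6.2.5 already gives for randomized subjects outside the safety set. Treat End of Treatment laboratory, ECG and nasal findings as on-treatment.
4. Show their AEs after dispensing as a separately flagged row or in a sensitivity table, not merged into the main on-treatment rates.

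The cost is SAP wording and a small programming change before lock, using CRF data already planned for collection. The drawback is that the dosing date stays unknown, so some events or findings may precede the dose, and a few devices recorded as used may not have delivered a full dose. Separate display keeps that uncertainty in view.
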